#### 11.2. Risk Minimization

The potential risks associated with the CCE were identified and have been successfully mitigated, as described in the PillCam COLON2 risk assessment file/documents. The overall residual risk has been determined to be acceptable. Any potential risks associated with this study are further minimized by selecting qualified and experienced investigators and training study personnel on the CIP.

In addition, investigators will be actively involved in the follow-up of the subjects undergoing the CCE procedure. Risks will be minimized by careful assessment of each subject prior to, during, and after the procedure.

The Sponsor has further minimized the possibility of risks by providing guidelines for subject selection and evaluation and providing adequate instructions and labeling.

The risks for CCE procedure, as noted, will be minimized by excluding subjects who have evidence of complicated medical or surgical histories that would otherwise preclude them from participating. In addition, subjects with sensitivity to substances used during the preparation for the CCE procedure will be excluded. Furthermore, training on the CIP screening, procedures, and follow-up will be given to all investigators and personnel included in the study.

Retention of the CCE capsule will be minimized since capsule will be administered only to those subjects who have no prior history of strictures, GI surgeries/diseases or major motility disorders. In addition, subjects with swallowing disorders are excluded to avoid the risk of capsule aspiration or inability to swallow the capsule.

## MDT20062 SPICE Clinical Investigation Plan Version 4.0 Version Date: 16Jun2022 Page 37 of 75 Medtronic

Table 2- Potential risks and risk minimization for study subjects

Potential risk	Risk Minimization
Capsule retention/bowel	Capsule retention is a known complication of CE. Physicians are
obstruction	trained to identify those patients who may be at increased risk
	for retention, including some who may be covered by the
	contraindication for CCE with suspected or known bowel
	obstruction. All subjects with prior GI histories, including
	surgeries, strictures, prior obstructions, or who are otherwise at
	risk or contraindicated for CCE will be excluded per the
	exclusion criteria.
Capsule aspirated instead of	Aspiration of the capsule has been reported as rare
swallowed	complication of CE. This risk is mitigated by the contraindication
	to use of the device with any patient with a swallowing
	disorder. In addition, ingestion of the capsule is usually
	performed under medical supervision.

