#### 9.2. Subject Enrollment

Written ICF will be obtained from each subject prior to performing any screening assessments. Once ICF is obtained, subjects will be screened to ensure they meet all of eligibility criteria prior to study enrollment. A subject is considered enrolled in the study once the ICF is signed and it is determined that all eligibility criteria are met.

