#### 9.3. Inclusion Criteria

- 1. Male or female adults ages 45-75 years
- 2. Subject is classified as being at high risk for CRC due to one (or more) of the following risk factors:
  - A personal history of colorectal polyps
  - A first-degree family history of colorectal cancer
  - Family/personal inherited syndrome (Lynch syndrome, Familial adenomatous polyposis {FAP}, other inherited syndromes linked to colorectal cancer)
  - Subject with currently suspected or diagnosed rectal bleeding, including positive FIT or positive fecal DNA test
  - Subjects under surveillance for CRC (last OC≥1.5 years)
- 3. Subject is willing and able to participate in study procedures, understand and sign the informed consent

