#### 9.4. Exclusion Criteria

- 1. Subject has a previous history or suspicion of inflammatory bowel or Crohn's disease, ulcerative Colitis or indeterminant Colitis
- 2. Subject has congestive heart failure or recent myocardial infarction (<3month)
- 3. Subject with moderate/severe renal disease and/ or severe hepatic impairment
- 4. Subject has uncontrolled diabetes
- 5. Subject has a severe, life-threatening disease
- 6. Subject with known gastrointestinal motility disorders
- 7. Subject has known delayed gastric emptying

- 8. Subject has undergone surgery of the luminal gastrointestinal (GI) tract, from esophagus to the rectum, other than uncomplicated appendectomy or cholecystectomy.
- 9. Subject with any current condition believed to have an increased risk of capsule retention such as suspected or known bowel obstruction or pseudo-obstruction, stricture, or fistula (symptoms such as severe abdominal pain with accompanying nausea or vomiting)
- 10. Subject with dysphagia, any swallowing disorder, or any major gastrointestinal motility disorder
- 11. Subject has a history of inadequate bowel preparation for colon imaging with colonoscopy, CTC, CCE, or DCBE (self-reporting)
- 12. Subject with known or suspected constipation history as defined by the following: as needing the use of medication (prescription or OTC) for management of constipation, or fewer than 3 BM/week regardless of medication use
- 13. Subject with a cardiac pacemaker or other implanted electromedical device
- 14. Subject with planned MRI examination within 7 days after ingestion of the capsule
- 15. The subject is taking antidepressant medicine or a medicine for psychiatric illness, such as:
  - selective serotonin reuptake inhibitor (SSRI)- as fluoxetine, fluvoxamine, paroxetine, sertraline, citalopram, escitalopram and zimeldine; - bupropion, venlafaxine, mirtazapine, clomipramine, buspirone; -
  - medicines classified as Monamine Oxidase Inhibitors (often used for treating depression).
- 16. Subject has glucose-6-phosphate dehydrogenase (G6PD) deficiency and/or allergic to peanut/soya
- 17. Subject consumes any of the medicinal products which interacts with MB-MMX, as per MB-MMX label and Investigator's discretion
- 18. Subject with allergies or known contraindication to the device, medications or preparation agents used in the procedure as described in the relevant instructions for use/ package inserts

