## MDT20062 SPICE Clinical Investigation Plan Version 4.0 Version Date: 16Jun2022 Page 28 of 75 Medtronic

#### 10.2. Subject Screening (visit 1)

All subjects that are considered for the study should be included on the study screening log. The reason for non-eligibility, as determined by the Investigator, should be recorded on the study screening log. The screening log serves as a method for the Sponsor to assess selection bias in the trial.

During the screening visit, the investigator will obtain patient's written informed consent, after the subject had an ample time and opportunity to read and understand the ICF, verify that the subject does not have any contraindications for the PillCam™ Capsule Endoscopy procedure, and assess each subject for eligibility based on the inclusion/exclusion criteria.

To determine subject eligibility, baseline information will be collected as outlined in Table 1- Schedule of events and data collection:. Informed consent, vital signs, medical history, concomitant medications, urine pregnancy test (performed in women with childbearing potential) and demographic information will be collected during the visit. Study medications required for the preingestion procedure will be provided to eligible subjects during this visit.

Data of screen failure subjects will not be captured within the Electronic Case Report Form (eCRF). Their signed ICF and Inclusion-Exclusion criteria evaluation will be kept on site.

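### The risk section says subjects with past strictures or obstructions are excluded, but exclusion criterion 9 covers only current conditions

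*Protocol*

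**What the plan says.** Protocol 11.2 (Risk Minimization) describes how capsule retention will be kept rare: "capsule will be administered only to those subjects who have no prior history of strictures, GI surgeries/diseases or major motility disorders". Table 2 in the same section, in the row on retention and bowel obstruction, makes the same promise in broader terms. It begins "All subjects with prior GI histories, including" and continues "surgeries, strictures, prior obstructions, or who are otherwise at" risk, and says that these subjects are removed by the exclusion criteria.

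The exclusion criteria are in Protocol 9.4 and are repeated in the synopsis. The one that addresses retention is criterion 9, with the same wording in both places: "Subject with any current condition believed to have an increased risk of capsule retention such as suspected or known bowel obstruction". It goes on to list pseudo-obstruction, stricture and fistula.

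Enrolment runs on the criteria. Under 9.2 a subject is enrolled once consent is signed and "it is determined that all eligibility criteria are met". At visit 1 (10.2) the investigator must "verify that the subject does not have any contraindications" to the capsule procedure and "assess each subject for eligibility based on the inclusion/exclusion criteria".

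**The concern.** The risk section speaks of history and the criterion speaks of the present. Table 2 does not merely describe an aim; it names the exclusion criteria as the means of exclusion, and those criteria contain no such rule. A subject with a known past stricture or obstruction could satisfy every listed criterion and receive the capsule, while the protocol tells the ethics committee that such a person would not.

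What is at stake is safety. Section 11.1 lists retention, obstruction and perforation among the potential events and notes that removal of the capsule has sometimes needed an intervention. Section 11.3 says participation may bring no direct benefit. The retention safeguard that is stated should therefore be the one that operates at enrolment.

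**Working it through.** No arithmetic on risk is possible, so the check compares the texts.

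**Step 1. Find every criterion that names stricture or obstruction.** Of the 24 exclusion criteria in 9.4, one does: criterion 9. It is limited to a *current* condition, and the synopsis copy carries the same limit.

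**Step 2. Is that limit deliberate wording or loose drafting?** Elsewhere the list uses history wording where history is meant: criterion 1 (previous inflammatory bowel disease), criterion 8 (past luminal surgery) and criterion 11 (past inadequate bowel preparation). Beside these, *current* in criterion 9 reads as a restriction.

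**Step 3. See what the other criteria catch.**
- Criterion 1 removes strictures due to inflammatory bowel disease.
- Criterion 8 removes strictures or obstructions treated by luminal GI surgery.
- Criterion 18 removes known device contraindications. Table 2 describes the contraindication as suspected or known obstruction and does not mention a resolved one. The user manual is not among the documents.
- Criterion 22 concerns the ability to comply, not retention.

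What remains is a resolved stricture or obstruction, not due to inflammatory bowel disease and managed without luminal surgery. It is excluded only if the investigator believes a current retention risk persists, or finds a device contraindication.

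**Step 4. Set each history named in the retention text against 9.4.**

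| History | Named in | Rule in 9.4 | Result |
|---|---|---|---|
| GI surgery | 11.2 text and Table 2 | Criterion 8, with an exception for uncomplicated removal of the appendix or gallbladder | Matched, but the exception is missing from the risk text |
| Motility disorder | 11.2 text | Criteria 6 and 10 | Matched |
| Stricture | 11.2 text and Table 2 | Criterion 9 | Only when current |
| Obstruction | Table 2 | Criterion 9 | Only when current |
| GI disease or GI history in general | 11.2 text and Table 2 | None as such | Literal conflict with inclusion criterion 2 |

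The tally is 2 matched + 2 matched only when current + 1 in conflict = 5.

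**Step 5. Look at the conflict in the last row.** Inclusion criterion 2 (9.3) has five bullets. Three can describe the subject's own GI disease or history: "A personal history of colorectal polyps", a personal inherited syndrome such as FAP, and rectal bleeding. Read literally, a rule against all GI disease or GI history would shut out people the study sets out to recruit. The risk section therefore cannot stand in for the criteria as the operating rule.

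**Step 6. Ask what happens if such a subject is dosed.** Section 10.14 treats any departure from the protocol as a deviation, so the case might be reported as one. It would not be a major eligibility deviation, because no listed criterion is breached.

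**The case against.** The strongest reply is that the risk section is a loose summary and 9.4 is the rule, so only 11.2 and Table 2 need correcting. On that view it is inconsistent to treat the stricture and obstruction wording as binding while dismissing the wording about GI diseases in the same sentences. There is a reason for the difference: a history of stricture or obstruction can be added to criterion 9 without contradicting anything, whereas a ban on GI disease in general contradicts inclusion criterion 2. If the sponsor did intend the current-only rule, though, the risk text is what is wrong, and it still has to change.

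Second, criterion 9 is risk-based and its examples are not exhaustive, so a past stricture that leaves a narrowing is already covered. The investigator is an experienced gastroenterologist trained on the system (8.1). This stands, and it is why the gap is narrow. It does not turn a judgement into the categorical exclusion that Table 2 claims.

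Third, the device instructions may already contraindicate a past stricture, which criterion 18 and the visit 1 check would then catch. This cannot be settled from the documents. The mismatch in the text does not depend on it.

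Fourth, follow-up limits the harm: 10.5 verifies excretion and provides for X-ray evaluation. That stands in part. The evaluation in 10.5 applies only when excretion is unreported and the capsule did not reach the colon, and the same section treats retention risk as nil once the colon is entered. A capsule held at a colonic narrowing would not trigger it, although 7.5 and 10.8 still allow an X-ray at discretion.

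**Conclusion.** The concern holds. Table 2 and 11.2 state a retention safeguard based on history, and the list used to enrol delivers it only for current conditions. The subgroup concerned is narrow: known, resolved strictures or obstructions that were neither due to inflammatory bowel disease nor treated by luminal surgery. Its size and its retention risk cannot be estimated, because the documents give neither the prevalence of such histories nor a retention rate. The tally of five histories shows where the texts diverge and does not measure risk. At most 15 subjects are planned, and no endpoint or analysis is affected. The conclusion rests on reading *current* in criterion 9 as a limit, which the history wording of criteria 1, 8 and 11 supports. Whether the device instructions close the gap through criterion 18 is unknown. The correction should be made, on grounds of subject safety and consistency.

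**What to change.** Amend criterion 9 in 9.4 and in the synopsis so that it opens with a subject who has a known history of bowel obstruction or stricture, followed by *or* and then the present wording unchanged. In the same amendment, reword the general references to GI surgeries and diseases (11.2) and to prior GI histories (Table 2) so that they describe the actual criteria, including criterion 8's exception.

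If the sponsor wants to keep the current-only rule, the alternative is to correct 11.2 and Table 2 so that they no longer claim an exclusion based on history. That makes the document consistent but gives up the stated safeguard.

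The cost is wording in four places and one amendment, which under 15.6 needs ethics committee approval, and regulatory approval where applicable, before use. Medical history is already taken at visit 1, so no procedure is added. A few candidates with a known resolved stricture or obstruction may be lost. The change protects only subjects not yet enrolled; SAP 7.1.3 shows that at least the first 5 had already received the earlier preparation regimen, which leaves at most 15 − 5 = 10.

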#### 11.3. Potential Benefits

The study participation may offer no direct benefit, as this is a pilot study, which does not include medical evaluation. Subject would be contributing to future knowledge and potential improvement in colonic polyp identification in the future during CCE procedure.

For the specific type of population included in the study (high risk for CRC), there might be a benefit related to the frequency of their standard of care CRC surveillance. The CCE procedure in between their surveillance Colonoscopy procedures, may offer additional information such as visualization of lesions which were missed during Colonoscopy and/or visualization of small lesions which might have malignancy potential. This is a non-invasive procedure which does not involve sedation nor bowel insufflation.

Due to the use of MB-MMX in conjunction with the CCE procedure, an additional benefit to the subject could be considered, as the MB-MMX has been found potentially effective in colonic polyp enhancement.

#### 11.4. Risk-Benefit Rationale

CCE procedure is considered as a safe, feasible, procedure for visualization of the colon, and offers a more convenient with relatively low risks than other invasive colon exams.

PillCam™ capsule and the corresponding endoscopy systems, have been cleared for marketing in many countries world-wide, including USA, EU, Canada, Japan and Australia. All capsules are considered as class IIa devices in Europe. Risk assessment has been performed and no major or intolerable risks were found.

All the mitigations as biocompatibility test, electrical safety and electromagnetic safety were documented according to ISO 14971. In addition, sponsor facilities have been certified to relevant medical device quality system requirements. The risk management summary demonstrates that the

## MDT20062 SPICE Clinical Investigation Plan Version 4.0 Version Date: 16Jun2022 Page 38 of 75 Medtronic

risks associated with the tested device are well mitigated and the residual risks are as low as reasonably practicable as defined by the applicable standards.

To conclude, the risks to subjects participating in this study would be similar to the expected risks for CRC surveillance subjects in standard medical practice, while the subjects can potentially benefit from better colonic polyps enhancement and the data gathered from this study could contribute to future knowledge and potential improvement in colonic polyps identification in future CCE procedures.

#### 12. Adverse Events and Device Deficiencies

#### 12.1. Adverse Events

AEs definitions are provided in Table 3- Adverse Event and Device Deficiency Definitions.

Adverse Events will be collected for all enrolled subjects at the start of the bowel preparation, at day (-1), until the follow-up phone call (visit 3). Medical care will be provided, as defined in the informed consent, for any AE related to study participation, if needed.

Reporting of these events to the Sponsor will occur on an AE Form. Each event must be reported separately. Documented pre-existing conditions are not considered AEs unless the nature or severity of the condition has worsened. Also, Diarrhea<24h after the CCE and mild anal burning/irritation are considered as the expected outcome of the bowel preparation process and shall not be recorded as Adverse Events, as long as the event does not require any medical intervention. Incidental findings observed during CCE video analysis will not be considered as AEs and will not be reported as such. In addition, in case of discovering a pregnancy during the course of the study, it will not be considered as an AE and will not be reported as such.

Per ISO14155:2020, it is required to collect all AEs and DDs. Non-subject AEs are not expected in this study, thus are not collected.

For AEs that require immediate reporting, initial reporting may be done by phone, fax, or on the eCRF completing as much information as possible. The completed AE eCRF must be submitted to the Sponsor as soon as possible.

Any medication/treatment associated with the treatment of an AE must be reported.

Subject deaths are also required to be reported. Refer to Section 12.6 for Subject Death collection and reporting requirements.

#### 12.2. Device Deficiency (DD)

The DD definition is provided in Table 3. DD information will be collected throughout the study and reported to Medtronic. Note that DD that result in an AE to the subject should be captured as an AE only.

DD that did not lead to an AE but could have led to a SADE (i.e., if suitable action had not been taken, if intervention had not been made, or if the circumstances had been less fortunate) require immediate reporting (

# MDT20062 SPICE Clinical Investigation Plan Version 4.0 Version Date: 16Jun2022 Page 39 of 75 Medtronic

Table 6: Reporting Requirements).

#### 12.3. Processing Updates and Resolution

For any changes in status of a previously reported adverse event or DD (i.e. change in actions taken, change in outcome, change in relatedness), information needs to be updated on, or added to the original AE or DD form. All AEs must be followed until the AE has been resolved, is unresolved with no further actions planned, the subject dies or exits the study, or until study closure, whichever occurs first.

If the subject is exited from the study prior to study completion, all efforts should be made to continue following the subject until all unresolved device or procedure related AEs, as classified by the investigator, are resolved, unresolved with no further actions planned, or study closure, whichever occurs first.

At the time of study exit, all collected adverse events that are unresolved must be reviewed and an update to the original AE must be reported.

#### 12.4. Definitions/Classifications

For the list of anticipated adverse events and anticipated adverse device effects, please refer to section 11.

**Table 3- Adverse Event and Device Deficiency Definitions** 

	General
Adverse Event (AE)	Untoward medical occurrence, unintended disease or injury, or untoward clinical signs (including abnormal laboratory findings) in subjects, users or other persons, whether or not related to the investigational medical device and whether anticipated or unanticipated  NOTE 1: This definition includes events related to the investigational medical device or the comparator.  NOTE 2: This definition includes events related to the procedures involved.  NOTE 3: For users or other persons, this definition is restricted to events related to the use of investigational medical devices or comparators.  (ISO 14155:2020, 3.2)
Adverse Device Effect (ADE)	AE related to the use of an investigational medical device  NOTE 1: This definition includes AEs resulting from insufficient or inadequate instructions for use, deployment, implantation, installation, or operation, or any malfunction of the investigational medical device.  NOTE 2: This definition includes any event resulting from use error or from intentional misuse of the investigational medical device.  NOTE 3: this includes 'comparator' if the comparator is a medical device.  (ISO 14155:2020, 3.1)

MDT20062 SPICE Clinical Investigation Plan			
Version 4.0	Version Date: 16Jun2022	Page 40 of 75	Medtronic

Inadequacy of a medical device with respect to its identity, quality, durability, reliability, usability, safety or performance.  NOTE 1: DD include malfunctions, use errors and inadequacy in the information supplied by the manufacturer including labeling.  NOTE2: This definition includes device deficiencies related to the investigational medical device or the comparator. (ISO 14155:2020, 3.19)
Relatedness
An AE that results from the presence or performance of any component of the device.  Device-related: An AE that results from the presence or performance (intended or otherwise) of the device.
An AE that occurs due to any procedure related to the CCE procedure (other than device). The preparation procedure for the CCE procedure in the study includes consumption of bowel preparation materials and MB-MMX tablets (non-MDT products).
Seriousness
AE that led to any of the following  a) death, b) serious deterioration in the health of the subject, users or other persons as defined by one or more of the following:  1) a life-threatening illness or injury, or 2) a permanent impairment of a body structure or a body function, including chronic disease, or 3) in-patient or prolonged hospitalization, or 4) medical or surgical intervention to prevent life-threatening illness or injury, or permanent impairment to a body structure or a body function, c) foetal distress, foetal death, a congenital abnormality, or birth defect including physical or mental impairment NOTE 1: Planned hospitalization for a pre-existing condition, or a procedure required by the CIP, without serious deterioration in health, is not considered an SAE. (ISO 14155:2020, 3.45)
Adverse device effect that has resulted in any of the consequences characteristic of a serious adverse event.  (ISO 14155:2020, 3.44)

MDT20062 SPICE Clinical Investigation Plan			
Version 4.0	Version 4.0 Version Date: 16Jun2022 Page 41 of 75		Medtronic

Serious Health	Signal from any adverse event or device deficiency that indicates an
Threat	imminent risk of death or a serious deterioration in the health in subjects,
	users or other persons, and that requires prompt remedial action for
	other subjects, users or other persons
	NOTE 1: This would include events that are of significant and unexpected
	nature such that they become alarming as a potential serious health
	hazard or possibility of multiple deaths occurring at short intervals.
	(ISO 14155:2020, 3.46)

